#### 7. SAFETY ANALYSIS

All safety summaries will be conducted using the SAS.

CONFIDENTIAL Page 16 of 28

# 7.1 Extent of Exposure

The expected and actual dose of SB-913, and the reasons for infusion interruption will be summarized and presented in a table.

A listing will also be provided.

#### 7.2 Adverse Events

#### 7.2.1 Treatment-emergent Adverse Events

A TEAE is any AE with an onset from the date of SB-913 infusion through the last study visit, whether or not it is considered causally related to the study drug.

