6.3 Baseline

Baseline assessments will be performed within 21 days prior to SB-913 infusion.

In subjects receiving ERT, ERT shall be withheld during the week of the administration of SB-913 to enable accurate baseline testing.

- Review and record concomitant medications.
- Physical examination.
- Vital signs.
- Assessment of AEs.
- ERT administration log.
- Joint range of motion (JROM).

- Neurologic cranial nerve exam and muscle strength testing of the upper extremities.
- 12-lead ECG.
- Pregnancy test (for females of childbearing potential only).
- Clinical laboratory tests.
- Liver panel.
- GAG testing in urine.
- IDS / GAG testing in blood.
- Vector genome PCR in plasma, saliva, urine, stool, and semen (males only).
- PFTs.
- 6-minute walk test (6MWT).
- Neurocognitive abilities tests by WASI-II (Wechsler Abbreviated Scale of Intelligence), WPPSI-IV (Wechsler Preschool and Primary Scale of Intelligence), or BSID-III (Bayley Scales of Infant Development), and by VABS-II.
- MRI of brain and cervical spine.
- Adrenocorticotropic hormone (ACTH) stimulation (cosyntropin) test (prior to prednisone or equivalent corticosteroid).
- Liver biopsy.
- Lumbar puncture.
- Immunogenicity assays.
- Prednisone or equivalent corticosteroid administration (starting 2 days before SB-913 infusion).

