10. SAFETY MONITORING AND ADVERSE EVENTS

10.1 Definitions

10.1.1 Adverse Event

An adverse event (AE) is any untoward medical occurrence in a patient or a clinical trial subject administered a medicinal product. An AE does not necessarily have a causal relationship with the administered treatment. The term can include any of the following events that develop or increase in severity during the course of the study:

- Any sign, symptom, or physical examination finding that worsens in nature, severity, or frequency compared to Baseline, whether thought to be related or unrelated to the condition under study.
- Any clinically significant laboratory abnormality or laboratory abnormality that requires medication or hospitalization.
- All reactions associated with the use of the study treatment, including those occurring as a result of an overdose, abuse, withdrawal phenomena, sensitivity, or toxicity to the study treatment.
- Concurrent illness.
- Injury or accident.

A pre-existing condition is one that is present prior to or at the start of the study, and is to be reported as part of the subject's medical history. It should be reported as an AE only if the frequency, intensity, or the character of the condition worsens during study participation.

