10.2 Adverse Event Reporting Period

AEs will be monitored continuously during the study from the time that the subject has provided written informed consent through the subject's last day of study participation. Subjects will be queried and events will be assessed at each clinic visit. A treatment-emergent AE (TEAE) is any AE with an onset from any time from administration of the study treatment through the last study visit, whether or not it is considered causally related to the study treatment.

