10.3 Recording of an Adverse Event

The Principal Investigator is responsible for evaluating all AEs, obtaining supporting documents, and determining that documentation of the event is adequate. He/she is responsible for determining the severity of the AE and its relationship to the investigational drug. The Principal Investigator may delegate these duties to sub-investigators but must assure that these sub-investigators are qualified to perform these duties under the supervision of the Principal Investigator.

All AEs will be recorded in the subject's CRF. The detailed description of the event will include appropriately graded severity of the AE and its relationship to the investigational product. Severity will be categorized by toxicity grade according to the Common Terminology Criteria for Adverse Events (CTCAE) Version 4.03.

AEs not listed in the Common Terminology Criteria for Adverse Events version 4.03 will be evaluated by using the following criteria:

- Grade 1, Mild: Symptoms cause no or minimal interference with usual social and functional activities.
- Grade 2, Moderate: Symptoms cause greater than minimal interference with usual social and functional activities.
- Grade 3, Severe: Symptoms cause inability to perform usual social and functional activities.
- Grade 4, Potentially Life-threatening: Symptoms cause inability to perform basic self-care functions OR medical or operative intervention indicated to prevent permanent impairment, persistent disability, or death.
- Grade 5: Outcome of AE is death.

The relationship of the AE to the investigational drug will be determined by the Principal Investigator. Any AE that does not meet the definition of a suspected AR will be categorized as Not Related.

Any Grade 3 and 4 clinical laboratory results that represents an increase in severity from Baseline will be reported as an AE if it is not associated with a diagnosis already reported on the CRF. A Grade 1 or 2 clinical laboratory abnormality should be reported as an AE only if it is considered clinically significant by the Principal Investigator.

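### The TEAE definition rests on onset alone, so an AE recorded before infusion that worsens after SB-913 may be left out of the primary endpoint and the AE summary tables

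*SAP*

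**What the plan says.** The primary endpoint is the incidence of TEAEs, including SAEs (protocol 13.4, SAP 2.2.1). SAP 7.2.1 defines the term: "A TEAE is any AE with an onset from the date of SB-913 infusion through the last study visit". Protocol 10.2 has: "A treatment-emergent AE (TEAE) is any AE with an onset from any time from administration of the study treatment through the last study visit". Both apply whether or not the event is thought to be related, and both depend only on when the event began.

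AE collection starts earlier, "from the time that the subject has provided written informed consent" (protocol 10.2). Protocol 10.1.1 describes AEs as covering "events that develop or increase in severity during the course of the study", and includes "Any sign, symptom, or physical examination finding that worsens in nature, severity, or frequency compared to Baseline". On a pre-existing condition the same section says: "It should be reported as an AE only if the frequency, intensity, or the character of the condition worsens during study participation". On laboratory results, protocol 10.3 says: "Any Grade 3 and 4 clinical laboratory results that represents an increase in severity from Baseline will be reported as an AE", with an exception for results tied to a diagnosis already on the CRF.

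In the severity summaries, each AE is shown at its maximum reported grade (protocol 13.4, SAP 2.2.1). All the AE summary tables in SAP 7.2.5 are built on TEAEs. The same section also plans a listing of every AE from consent, with a TEAE flag.

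**The concern.** Several things happen before infusion that can open an AE record. The Baseline list in protocol 6.3 includes a liver biopsy, a lumbar puncture and "Prednisone or equivalent corticosteroid administration (starting 2 days before SB-913 infusion"). An event that begins then and is still open at infusion has a pre-infusion onset date. If it later rises from Grade 1 to Grade 3, or becomes serious, an onset-only rule does not see the change.

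Neither document says whether such a worsening is a new AE with its own onset date or a grade update on the old record. Whether it counts in the primary endpoint therefore depends on site data-entry practice that the plan leaves open. Deterioration after a single gene-editing infusion is what a first-in-human safety endpoint should capture. The rows at stake are any TEAE, Grade 3 or higher, related, leading to withdrawal, leading to death, and treatment-emergent SAE.

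**Working it through.** **Sample size.** The plan's only relevant figure is its maximum enrolment: 8 cohorts × (2 + 2) = 32, which matches protocol 13.1. The documents give no expected TEAE incidence and no length for the pre-infusion AE period.

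**Length of the pre-infusion AE period.** Screening may take up to about 3 months (protocol 6.1) and falls within 3 months of Baseline (Appendix 1). Baseline assessments fall within 21 days before infusion (protocol 6.3).
- 3 × 365.25 / 12 = 91.3 days
- 91.3 + 21 = 112.3 days
- 112.3 / 7 = 16.0 weeks

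With 4-week months the result is 12 + 3 = 15 weeks. Either figure is a maximum, not a typical value.

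**Tracing one event.** Take an AE recorded at Grade 1 before infusion that reaches Grade 3 afterwards.
- *Grade update on the same record.* The onset stays before infusion, so it is not a TEAE under either definition. It is absent from every summary table in SAP 7.2.5. The listing shows it, but not flagged as a TEAE.
- *New record at worsening.* The onset is after infusion, so it is a TEAE and is counted at Grade 3.

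**Which handling the text favours.** Nothing decides it, but some wording leans towards the single record:
- The maximum-severity rule presupposes that one AE can carry more than one grade.
- The laboratory rule in protocol 10.3 does not call for a new AE when the result belongs to a diagnosis already on the CRF.
- The listing in SAP 7.2.5 has onset and resolution dates but no date of grade change.

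Against that, protocol 10.1.1 lets worsening compared with Baseline be an AE in itself.

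**Effect of one reclassified subject on a row** (100 / n, if that subject has no other event in the row):
- n = 2: 50 percentage points
- n = 4: 25 points
- n = 16 (all cohorts at 2): 6.25 points
- n = 32 (maximum enrolment): 3.1 points

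**Day 0.** The protocol's cut is administration of the study treatment; the SAP's is the date of infusion. An event that starts on Day 0 before the infusion is a TEAE under the SAP but not under the protocol. The listing carries date and day of onset, not time.

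**The case against.** The strongest defence is that exclusion is possible, not certain. A reader might infer that every post-infusion worsening of an earlier AE is removed, whatever its grade. The documents do not support that: protocol 10.1.1 allows worsening against Baseline to be an AE, and protocol 10.3 requires it for Grade 3 and 4 laboratory increases outside an already reported diagnosis. Entered with its own post-infusion onset, such an event meets both TEAE definitions. CRF instructions, which are not among the documents, might settle the handling. This part of the defence stands.

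A reader might also infer that the TEAE definition contradicts the AE definition. It does not. Protocol 10.1.1 says what an AE is and 10.2 says which AEs are treatment-emergent; the SAP follows the protocol in using onset. The two sections have not been reconciled on how a worsened event is dated.

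Nor do these events vanish from the reporting. The all-AE listing keeps them. Laboratory worsening also appears in the change-from-baseline summaries and the per-subject liver figures (SAP 7.3). The SMC triggers (protocol 12.3, SAP 8) are worded on AEs and SAEs, not TEAEs. Conditions present at study start go to medical history and are reported as AEs when they worsen. The exposed group is therefore narrow: AEs first recorded between consent and infusion, still open at infusion, worsening later, and handled as a grade update.

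Finally, the 50-point shift is less likely in the any-TEAE row, because a subject followed for up to 36 months may well have another TEAE. It is more plausible in a Grade 3 or higher, SAE or single preferred-term row.

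These points limit the consequence but do not remove the gap. No summary table of all AEs backs up the TEAE tables. Protocol 13.4 promises a summary of all SAEs, whereas the SAP 7.2.5 table covers only treatment-emergent ones.

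**Conclusion.** The point holds as a gap in the definition. Both TEAE definitions lack a worsening clause, and no rule dates a post-infusion worsening of an AE already on record. Where sites update the existing record, the event drops out of the primary endpoint and all the TEAE-based tables, while remaining in the listing and available to the SMC.

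The size is conditional: 50 percentage points in a cohort of 2 and 25 in a cohort of 4 per affected subject, provided that subject has no other event in the row. The number of affected subjects cannot be derived. The study is descriptive, so no test or sample size is affected. The Day 0 difference is real but minor, and the SAP's version errs towards inclusion. A worsening clause should be added: it is cheap and makes the endpoint independent of recording habit.

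**What to change.** - **Protocol 10.2 and SAP 7.2.1.** Define a TEAE as an AE with onset at or after the SB-913 infusion, or with earlier onset that increases in CTCAE grade or becomes serious after the infusion.
- **SAP 7.2.5.** For events in the second group, tabulate the highest post-infusion grade.
- **CRF instruction.** Tell sites either to open a new AE record at worsening or to enter the date of grade increase on the existing one. Choose one method for all sites, because the overall table in SAP 7.2.5 also counts episodes.
- **Day 0.** Use one cut in both documents, for example counting Day 0 events as TEAEs unless they are recorded as starting before the infusion.

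The cost is wording in two documents, one programming rule and a small CRF instruction. TEAE counts may rise slightly. A cut based on clock time could need an added CRF field, since the planned listing has no onset time. Sample size, visits and treatment do not change.

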# 7.2.2 Adverse Event Severity

Severity will be categorized by toxicity grade according to the Common Terminology Criteria for Adverse Events (CTCAE) Version 4.03. AEs not listed in the CTCAE v4.03 will be evaluated by using the following criteria:

- Grade 1, Mild: Symptoms cause no or minimal interference with usual social and functional activities
- Grade 2, Moderate: Symptoms cause greater than minimal interference with usual social and functional activities
- Grade 3, Severe: Symptoms cause inability to perform usual social and functional activities
- Grade 4, Potentially Life-threatening: Symptoms cause inability to perform basic self-care functions OR medical or operative intervention indicated to prevent permanent impairment, persistent disability, or death
- Grade 5: Outcome of AE is death

# 7.2.3 Adverse Event Relationship to Study Medication

The relationship of the AE to the investigational drug will be categorized by the Principal Investigator as Related or Not Related. Any AE that does not meet the definition of a suspected Adverse Reaction will be categorized as Not Related.

#### 7.2.4 Serious Adverse Events

An AE or Suspected Adverse Reaction is considered serious if, in the view of either the Principal Investigator or Sangamo, it results in any of the following outcomes:

- Death
- Life-threatening AE
- Inpatient hospitalization or prolongation of existing hospitalization
- Persistent or significant incapacity or substantial disruption of the ability to conduct normal life function
- Congenital anomaly/birth defect in the offspring of an exposed subject

CONFIDENTIAL Page 17 of 28

#### 7.2.5 Adverse Event Summaries

For TEAEs, the following will be summarized and presented for the Safety Analysis Set overall and by dose cohort:

- i. An overall summary of TEAEs, which includes:
  - a. the number and percentage of subjects experiencing a TEAE
  - b. the number and percentage of subjects experiencing a TEAE equal to or greater than Grade 3 toxicity
  - c. the number and percentage of subjects experiencing a related TEAE
  - d. the number and percentage of subjects experiencing a TEAE leading to study withdrawal
  - e. the number and percentage of subjects experience a TEAE leading to death
  - f. the number and percentage of subjects experiencing a treatment emergent SAE (TESAE)
- ii. the number and percentage of subjects experiencing a TEAE by SOC and PT
- iii. the number and percentage of subjects experiencing a TEAE by SOC, PT and the highest toxicity grade
- iv. the number and percentage of subjects experiencing a TEAE by SOC, PT and the strongest relationship to study medication
- v. the number and percentage of subjects experiencing a TEAE by PT
- vi. the number and percentage of subjects experiencing a TEAE leading to study withdrawal by SOC and PT
- vii. the number and percentage of subjects experiencing a TESAE by SOC and PT

In the overall summary of TEAEs table (i), besides tabulating the number and percentage of subjects, the total number of TEAE episodes will also be provided. If a subject has repeated episodes of a particular TEAE, all episodes will be counted in the summary table.

In the remaining summary tables, the incidence of TEAEs will be calculated by dividing the number of subjects who have experienced the event by the total number of subjects in the Safety Analysis set. Thus, the incidence of TEAEs is shown in terms of the total number of subjects and not in terms of the total number of episodes. If a subject has repeated episodes of a particular TEAE, only the most severe episode, or the episode with the strongest causal relationship to study drug, will be counted in the summary tables.

A subject with more than one type of TEAE in a particular SOC will be counted only once in the total of subjects experiencing TEAEs in that particular SOC. Since a subject could have more than one type of TEAE within a particular SOC, the sum of subjects experiencing different TEAEs within the SOC could appear larger than the total number of subjects experiencing TEAEs in that SOC. Similarly, a subject who has experienced a TEAE in more than one SOC will be counted only once in the total number of subjects experiencing AEs in all SOCs. At each level of summation (relationship, toxicity grade), subjects reporting more than one TEAE are

CONFIDENTIAL Page 18 of 28

counted only once using the strongest relationship to study medication and highest toxicity grade.

All AEs (serious and non serious) occurring after completion of the informed consent process and before the end of study, regardless of relationship to study drug, will be included and classified by SOC and PT using MedDRA in a listing by subject, grouped by dose cohort.

The listing will contain the following information: dose cohort, verbatim term, SOC, PT, severity, toxicity grade, relationship to study medication, date and day of onset, date and day of resolution, treatment given to treat the adverse event, the outcome, whether the event was an SAE, whether it led to withdrawal and whether it is a TEAE. Listings will be sorted by subject identification number, onset date, SOC, and PT. If the onset date is completely missing, then these events will be presented first. If the onset date is missing a month or a day, then these events will be presented before any complete dates.

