10.4 Serious Adverse Event Reporting Period

All SAEs, whether or not unexpected or considered to be associated with the administration of study treatment, must be reported immediately to Sponsor or its designees, and must be submitted to Sponsor or its designees on an SAE Report form within 24 hours of the Principal Investigator's discovery of the event. Please refer to the study reference manual for SAE reporting guidelines and contacts.

The reporting period for all SAEs is from subject consenting through the last study visit.

The Principal Investigator is responsible for promptly notifying the IRB/IEC or equivalent in accordance with local regulations of all SAEs. The National Institutes of Health (NIH) requires that all investigators participating in gene transfer research to report all SUSARs. SUSARs will be reported to the appropriate regulatory authorities (FDA/MHRA or equivalent) according to the requirements for expedited safety reporting. Sangamo or its designee will assume the responsibility for reporting SUSARs to the FDA/MHRA or equivalent.

All "serious" events must be followed with appropriate medical management until resolved or stabilized.

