13.4 Primary Endpoint

The primary endpoint of this study is the incidence of treatment-emergent AEs (including SAEs).

Additional safety evaluations will include:

- Routine hematology, chemistry, and liver function laboratory tests, vital signs, physical exam, ECG, ECHO, and concomitant medications.
- Cranial nerve exam and muscle strength testing.
- Serial AFP testing and MRI of liver to evaluate for liver mass.

Safety assessment will be performed on all subjects. All reported AEs will be coded to a standard set of terms using the Medical Dictionary for Regulatory Activities (MedDRA).

Treatment-emergent adverse events will be summarized overall and by treatment cohort. For each subject, the maximum reported severity of each adverse event will be used in the summaries by

severity grade. In addition, all serious adverse events and AEs related to study treatment will be summarized.

Laboratory data will be summarized for each time-point at which specimens are collected. Change-from-Baseline values may be calculated for selected laboratory parameters. Shift-tables (Change-from-Baseline relative to the normal range) may be constructed for selected laboratory parameters.

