### 2.2 Endpoints

#### 2.2.1 Primary Endpoint

The primary endpoint of this study is the incidence of treatment-emergent adverse events (TEAEs) including serious adverse events (SAEs).

Additional safety evaluations will include:

- Routine hematology, chemistry, and liver function laboratory tests, vital signs, physical exam, electrocardiogram (ECG), echocardiogram (ECHO), and concomitant medications.
- Cranial nerve exam and muscle strength testing.
- Serial  $\alpha$ -fetoprotein (AFP) testing and magnetic resonance imaging (MRI) of liver to evaluate for liver mass.

CONFIDENTIAL Page 8 of 28

Safety assessment will be performed on all subjects. TEAEs will be summarized overall and by treatment cohort. For each subject, the maximum reported severity of each adverse event will be used in the summaries by severity grade. In addition, all SAEs and AEs related to study treatment will be summarized.

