# 4.2 Analysis Sets

All subjects enrolled in this study who receive any portion of the SB-913 infusion will be included in the Safety Analysis Set . All analyses (i.e., safety, primary, secondary, and exploratory) will be performed using the Safety Analysis Set .

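### The protocol and SAP promise a summary of all SAEs, but both SAE outputs in SAP 7.2.5 are treatment-emergent only, so SAEs with onset before the infusion date reach no summary table

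*SAP*

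**What the plan says.** **Collection.** Protocol 10.4 states: "The reporting period for all SAEs is from subject consenting through the last study visit".

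**The promised summary.** After describing the TEAE summaries, Protocol 13.4 continues: "In addition, all serious adverse events and AEs related to study treatment will be" summarised. SAP 2.2.1 repeats this: "In addition, all SAEs and AEs related to study treatment will be summarized". Neither sentence limits the SAEs to treatment-emergent ones.

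**What is programmed.** SAP 7.2.5 opens its list of outputs with "For TEAEs, the following will be summarized and presented for the Safety Analysis Set overall and by dose cohort". Two of the listed outputs concern SAEs: item i.f, an overall count of subjects with a treatment-emergent SAE, and item vii, "the number and percentage of subjects experiencing a TESAE by SOC and PT". Under SAP 7.2.1, "A TEAE is any AE with an onset from the date of SB-913 infusion through the last study visit".

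**Population.** The Safety Analysis Set in SAP 4.2 is the infused subjects, and "All analyses (i.e., safety, primary, secondary, and exploratory) will be performed using the Safety Analysis Set". Protocol section 13 uses the same infused-only population.

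**The listing.** SAP 7.2.5 also provides a by-subject listing of every AE from consent to the end of study, with flags for SAE and TEAE status.

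**The concern.** The period before infusion carries risk that the study itself imposes. Baseline, within 21 days before infusion, includes a liver biopsy and a lumbar puncture (Protocol 6.3), each required unless contraindicated (Protocol 9.28 and 9.29). The corticosteroid starts two days before infusion. A biopsy complication at Week 24 would be tabulated; the same complication at Baseline would not.

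The study's safety rules make no such distinction. Under Protocol 12.3 and SAP section 8, any SAE unrelated to the underlying disease convenes the SMC, whether or not it is treatment-emergent. A pre-infusion SAE could therefore convene the SMC and still be missing from every SAE table in the report.

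There is also a selection problem. The sample-size text (Protocol 13.1, SAP section 9) foresees subjects who are enrolled and not dosed. An SAE serious enough to prevent infusion takes its own subject out of the only analysis set. Safety is the sole primary objective and cohorts are planned at two subjects, so one untabulated SAE is not negligible.

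**Working it through.** The plan gives no figure to reproduce. The check compares the scope of each output with the promised summary, followed by a simple count.

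**1. Scope of the summary outputs**

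| Item | Onset covered | Subjects covered |
|---|---|---|
| SAE collection (Protocol 10.4) | from consent | all consented |
| Promised SAE summary (Protocol 13.4, SAP 2.2.1) | no onset limit stated | infused only, under Protocol 13 and SAP 4.2 |
| SAP 7.2.5, items i to vii | from the infusion date | infused only |
| SAP 7.2.5, all-AE listing | from consent | not stated; SAP 4.2 may limit it to infused |

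Of the seven summary outputs, 0 can contain an SAE with onset before the infusion date, and 0 can contain any SAE in a never-infused subject. The uncovered period runs from consent through Screening (about 3 months) and Baseline (up to 21 days) to the day before infusion.

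**2. The infusion day and the steroid.** The SAP rule works by date, so an SAE on Day 0 counts as treatment-emergent even if it began before the infusion. The protocol definition is slightly narrower: a TEAE "is any AE with an onset from any time from administration of the study treatment". Under the SAP rule, steroid-related SAEs are uncovered only if onset is on Day -2 or Day -1. Those during the rest of the roughly 20-week course are counted.

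**3. Procedures before infusion.** The Schedule of Events places liver biopsy and lumbar puncture at Baseline, Week 24 and Week 48. The share before infusion is (1 + 1)/(3 + 3) = 2/6 = 33%.

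Number of pre-infusion procedures = subjects × 2:
- planned minimum, 8 cohorts × 2 = 16 subjects: 16 × 2 = 32;
- ceiling, 32 subjects: 32 × 2 = 64.

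Both are maxima for their sample size, because either procedure is skipped if contraindicated.

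**4. Expected untabulated SAEs.** Expected events = procedures × SAE risk per procedure. The documents give no such risk. I assume 1% to 3%, the same for both procedures:
- 16 subjects: 32 × 0.01 = 0.32 to 32 × 0.03 = 0.96;
- 32 subjects: 64 × 0.01 = 0.64 to 64 × 0.03 = 1.92.

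The scope result in step 1 depends on none of these figures.

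**The case against.** **The events are listed anyway.** With two subjects planned per cohort, a flagged line listing conveys nearly as much as a table. This largely stands for infused subjects. A reader might infer that pre-infusion SAEs go unreported; the documents do not support that. Reporting to the sponsor within 24 hours (Protocol 10.4), SMC review and the listing all remain, and SAP 5.1 counts subjects enrolled and dosed. The gap is in tabulation. But a listing is not the promised summary, and for never-infused subjects the listing is not assured. Its sentence names no analysis set, while SAP 4.2 applies one set to all analyses. That they are excluded is a possible reading, not an established fact.

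**The promise can be read more narrowly.** The primary endpoint names SAEs as part of the treatment-emergent events, and the sentence on all SAEs directly follows the TEAE text, so it could mean treatment-emergent SAEs. It could also mean only SAEs related to treatment. The first reading is possible, but it leaves the words announcing an addition with little to add. Under the second, SAP 7.2.5 still has no table of related SAEs.

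**The infused-only population is the protocol's own.** This stands. A reader might infer that the SAP narrowed the population; it did not. The clear departure is the treatment-emergent limit.

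**The numbers lean on an outside rate.** This also stands. They indicate scale only.

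**Conclusion.** The point holds as a mismatch between a stated summary and the programmed outputs. On the natural reading of Protocol 13.4 and SAP 2.2.1, all SAEs are to be summarised; SAP 7.2.5 summarises only those from the infusion date onward. The SAEs left out include any from one third of the scheduled biopsies and lumbar punctures, and any steroid-related SAE on the two days before infusion.

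The size is modest: roughly 0.3 to 1.0 events expected at 16 subjects and 0.6 to 1.9 at 32. This rests on the assumed 1% to 3% risk per procedure and on every subject having both Baseline procedures. What changes is the reported SAE total.

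A reader might infer that the primary endpoint is undercounted. It is not, because that endpoint is treatment-emergent by definition. Nor is steroid harm generally missing, since onsets from Day 0 are counted. The correction is worth making because safety is the sole primary objective, cohorts are very small, and an SAE that prevents infusion removes its subject from the only analysis set.

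**What to change.** - **SAP 7.2.5:** keep the treatment-emergent SAE table. Add one SAE table or count from consent for all enrolled subjects, split into before infusion and from infusion to the last visit. The split is a proposal; neither Protocol 13.4 nor SAP 2.2.1 specifies it.
- **SAP 4.2:** state that this table and the all-AE listing include subjects enrolled but never infused, as an exception to the Safety Analysis Set rule.

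If the sponsor intended treatment-emergent SAEs only, the minimum repair is to say so in Protocol 13.4 and SAP 2.2.1 and to confirm that pre-infusion SAEs are listed for all enrolled subjects. That removes the mismatch but leaves these SAEs untabulated, so the added table is preferable.

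The cost is one extra table from data already collected. Pre-infusion events must be labelled as preceding SB-913 so that they are not read as product toxicity.
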